### 9.3 Secondary aims

Secondary outcome measures including (1) the evaluation of adverse events utilizing the NCI CTCATE v4.03, (2) complete response (no emesis and no rescue medication use), (3) characterization of 24-hour CINV using the MAT, (4) five-day health related quality of life utilizing the FLIE, and (5) healthcare resource utilization (emergency room visits, hospitalizations, and infusion center visits over seven days).

- (1) Adverse events will be recorded in detail and the number of events will be described using n and percent. The severity will be described using means (SD) and medians (IQR) of the adverse event grade (which ranges 0-5).
- (2) The proportion of patients experiencing complete response will be described with descriptive statistics (n and percent) as well as by using a one-sample confidence interval for proportions, applying the normal approximation to the binomial distribution. In addition, a one-sample z test for proportions will be used to determine if the complete response rate in this sample is significantly different than the 90% seen in previous studies.
- (3) CINV will be analyzed using the MAT. The MAT consists of 8 distinct items, 4 of these items are binary and will be described using n and percents the other 4 items are continuous (ranging from 0-10) and will be described using mean and SD. Binary variables will also be described using one-sample confidence intervals for proportions (as described in #2 above) and continuous variables will be described using one-sample confidence intervals for means.
- (4) Quality of life will be analyzed as a binary response, impact on quality of life vs no impact, a score of less than 54 on the FLIE domain scores and a score of less than 108 on the total score indicates an impact on quality of life. Each domain score, and the total score, will be analyzed separately using a 95% confidence interval to describe the proportion of participants with impacted QoL.
- (5) Healthcare resource utilization will be assessed by recording the number of emergency room visits, hospitalizations (with length of stay), and infusion center visits. Each healthcare utilization will be categorized with respect to whether it was specifically related to nausea and vomiting during the seven-day follow up period. A table summarizing the number of each type of utilization related to nausea and vomiting will be provided.

- 
- (6) The occurrence of refractory CINV will be analyzed using CINV risk assessment at follow up day 7 compared to treatment day 1.

Patient demographic characteristics (age, sex, and patient reported race/ethnicity) will be described using standard descriptive statistics (n/% or mean/SD).

As an exploratory aim, regression analysis will be used to develop a predictive model for CINV, based on age, sex, history of >1 alcoholic beverage per day, history of motion sickness, history of hyperemesis gravidarum, and history of anxiety.

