### **4.1 Subjects and Centers**

A total of 50 subjects, who are 18 years of age or older, have histologically confirmed cancer, confirmed refractory CINV as defined above, an ECOG performance status 0-2, and normal calcium level will be enrolled on this single-center, single-arm study.

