### **7.0 Safety Measures**

---

A physical examination and complete metabolic profile will be assessed at screening to evaluate for the presence of any pre-treatment abnormalities and to confirm eligibility. Physical examination and laboratory testing to evaluate adverse effects that develop during the seven-day treatment and follow-up periods will be performed according to routine frequency for monitoring of the subject's cancer according to the treating oncologist.

Subjects will also be monitored for evidence of QTc interval changes at screening (an EKG will be required prior to Akynzeo® treatment on C2D1) and during the study treatment period on Study Day 3±3 days with a single EKG. If the patient experiences any worsening cardiac symptoms, including, but not limited to dizziness, shortness of breath, or chest pain, during the study period, additional EKG(s) will be performed as clinically indicated.

Daily safety assessments will be performed on the day of Akynzeo® treatment (Study Day 1), and daily during the post-treatment observation portion of the study (Study Days 2-7). All adverse events will be graded according to National Cancer Institute Common Terminology Criteria for Adverse Events (CTCAE) version 4.03.10

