## 8.2 Severity

All adverse events will be graded according to the NCI CTCAE version 4.03. The CTCAE v4.03 is available at <http://ctep.cancer.gov/reporting/ctc.html>

Per CTCAE v 4.03 when no predefined grading is available, the severity of an AE is graded as follows:

- Grade 1 Mild; asymptomatic or mild symptoms; clinical or diagnostic observations only; intervention not indicated.
- Grade 2 Moderate; minimal, local or noninvasive intervention indicated; limiting age-appropriate instrumental ADL\*.
- Grade 3 Severe or medically significant but not immediately life-threatening; hospitalization or prolongation of hospitalization indicated; disabling; limiting self-care ADL\*\*.
- Grade 4 Life-threatening consequences; urgent intervention indicated.
- Grade 5 Death related to AE.
- \*Instrumental ADL refer to preparing meals, shopping for groceries or clothes, using the telephone, managing money, etc.
- \*\*Self care ADL refer to bathing, dressing and undressing, feeding self, using the toilet, taking medications, and not bedridden.

---

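### Adverse event severity is summarised by the mean and median of an ordinal grade, with unit and denominator undefined, so the plan never shows how many patients had a severe event

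*Combined protocol and SAP*

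**What the plan says.** Section 9.3, item (1), contains the whole adverse event analysis, and the Statistical Methodology part of the Study Summary repeats it. It has two parts.

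- Frequency: "Adverse events will be recorded in detail and the number of events will be described using n and percent". No denominator is given for the percentage, and there is no breakdown by grade or by patient.
- Severity: "The severity will be described using means (SD) and medians (IQR) of the adverse event grade (which ranges 0-5"). Neither the unit of analysis nor the denominator is stated.

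Section 8.2 sets out the severity scale for events without predefined grading. It starts at "Grade 1 Mild; asymptomatic or mild symptoms; clinical or diagnostic observations only; intervention not indicated" and ends at "Grade 5 Death related to AE". It has no grade 0, and no other section introduces one.

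Section 7.0 states how often events are sought, with observation ending on Day 7: "Daily safety assessments will be performed on the day of Akynzeo® treatment (Study Day 1), and daily during the post-treatment observation portion of the study". Section 4.1 gives the planned size: "A total of 50 subjects, who are 18 years of age or older, have histologically confirmed cancer". No section plans a table of patients by worst grade or a rate of grade 3 or higher events.

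**The concern.** Three features of the severity summary cause difficulty.

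- **Scale.** The grades are ordered categories running from mild to death. A mean treats the steps between them as equal, and it lets many low grades offset a few high ones.
- **Zero.** The stated range begins at 0, but a recorded event cannot have grade 0. A zero can therefore only stand for a patient with no event. The plan does not say whether such patients enter the summary.
- **Unit.** If each event is an observation, a patient with many mild records carries more weight than a patient with one severe event. If each patient is an observation, the result depends on how event-free patients are handled.

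Occurrence of adverse events is a secondary objective (Section 2.2). Section 1.3 says that nothing has been published on this drug for refractory CINV, and Section 5.3 intends the secondary results to inform a larger study. That study's planners will want to know how many patients had severe toxicity, and no planned output tells them.

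**Working it through.** The documents give no adverse event rate, expected grade or SD, so there is no stated figure to reproduce. Every distribution below is an assumption chosen for illustration. The inputs from the documents are the summary statistics (Section 9.3), grades 1 to 5 (Section 8.2) and N = 50 patients (Section 4.1).

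**Step 1: different severity profiles, same mean and median.** Mean grade = sum of (grade × count) / total count.

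| Assumed events | Mean | SD | Median (IQR) |
|---|---|---|---|
| 95 grade 1, 5 grade 4 | (95 + 20)/100 = 1.15 | 0.66 | 1 (1 to 1) |
| 85 grade 1, 15 grade 2 | (85 + 30)/100 = 1.15 | 0.36 | 1 (1 to 1) |
| 48 grade 1, 2 grade 5 | (48 + 10)/50 = 1.16 | 0.79 | 1 (1 to 1) |
| 42 grade 1, 8 grade 2 | (42 + 16)/50 = 1.16 | 0.37 | 1 (1 to 1) |

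The first pair differs by five life-threatening events and the second by two deaths. In all four rows fewer than a quarter of the events lie above grade 1, so the upper quartile stays at 1 and the median and IQR cannot respond. Only the SD moves, and an SD does not give a count of severe events.

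**Step 2: patient as unit, effect of scoring event-free patients 0.** Assume 20 of 50 patients affected, with worst grades 1/2/3/4 in 12/4/2/2 patients. The sum of grades is 12 + 8 + 6 + 8 = 34.

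- Affected patients only: 34/20 = 1.70 (SD 1.03), median 1.
- All patients, with 30 zeros: 34/50 = 0.68 (SD 1.06), median 0.

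Keep the same mix of grades and vary the number affected from 10 to 40. The affected-only mean stays at 1.70, while the all-patient mean runs from 17/50 = 0.34 to 68/50 = 1.36. One convention does not respond to how many patients are affected; the other mixes incidence with severity.

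**Step 3: event as unit, effect of repeated mild records.** Take the 20 graded events of Step 2, one per patient, and add 20 grade 1 records from one patient. The mean becomes (34 + 20)/40 = 1.35, down from 1.70. Patients with grade 3 or higher remain 4 of 50 (8%). Recording more toxicity has lowered the severity figure.

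**Step 4: what a per-patient count would show.** The Clopper-Pearson 95% limits for x of n are the 0.025 quantile of Beta(x, n − x + 1) and the 0.975 quantile of Beta(x + 1, n − x). With n = 50:

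| Patients with grade 3 or higher | Proportion | Exact 95% CI |
|---|---|---|
| 0 | 0% | 0% to 7.1% |
| 1 | 2% | 0.05% to 10.6% |
| 2 | 4% | 0.5% to 13.7% |
| 4 | 8% | 2.2% to 19.2% |

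**The case against.** The strongest defence is that this is a descriptive secondary summary. No test or interval is planned for adverse events, so repeated records from one patient bias no standard error or p value. That stands, and it limits the point to the quality of the description.

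Second, severe events would not go unnoticed. Section 8.1 has each event evaluated for grade, seriousness and relationship, and Section 8.6.1 sets expedited routes to the principal investigator, the FDA and the funder. This also stands as a limit: a reader might infer that the plan would conceal a life-threatening event, and the documents do not support that. But those routes are reporting duties, not analyses. Seriousness (Section 8.3) is also a different classification from grade, so a grade 3 event need not be a serious one.

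Third, the planned SD does separate the paired scenarios. It does, but a reader cannot recover from it how many patients had which grade.

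Some stronger readings are tempting and go too far.

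- A reader might infer that the event is the unit throughout. Section 9.3 counts events for frequency but names no unit for severity, and a range starting at 0 fits a patient-level score at least as well.
- A reader might infer that the dilution in Step 3 and the zero problem in Step 2 both operate. They belong to alternative readings: a per-event summary has no zeros, and a worst-grade-per-patient summary has no repeated records.
- A reader might infer that a mean equates one grade 4 event with four grade 1 events. That would be true of a summed score. A per-event mean gives 4 in one case and 1 in the other; the valid complaint is the assumed equal spacing.
- A reader might infer that extra mild events always lower the mean. If event-free patients score 0, each newly affected patient raises it.

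**Conclusion.** The concern holds. Followed exactly, Section 9.3 yields a severity summary that can be the same in mean, median and IQR with and without life-threatening events. Its value also depends on a unit and denominator that the plan leaves open: 1.70 or 0.68 for the same 20 of 50 affected patients. The 0 to 5 range has no counterpart in the grades of Section 8.2. This is more than a missing detail, because a standard and more informative summary is available from data the trial already collects.

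The effect is confined to the description of one secondary objective. It should be corrected before the analysis, but it does not touch the primary feasibility aim or the sample size. How far the planned summary would mislead in this trial depends on event counts and grades, for which the documents give no expected values. The scenarios show what can happen, not what is likely.

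**What to change.** In Section 9.3, item (1), and in the matching text of the Study Summary:

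- Replace the mean (SD) and median (IQR) of grade with the number and percentage of dosed patients by worst grade (none, 1, 2, 3, 4, 5), overall and by CTCAE term.
- Report the proportion of dosed patients with any grade 3 or higher event, with an exact 95% confidence interval.
- Keep event counts as a listing.

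Patients without events then have their own row, so grade 0 is no longer needed. If a version restricted to related events is added, the causality scale must be reconciled first: Section 8.4 has two levels and Section 9.4 has five. The table should also name its collection window, because Section 8.1 follows events up to 30 days after the last dose while the Schedule of Events marks monitoring on Study Days 1 to 7.

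The core change costs a few lines of text and one standard table. It needs no new data and no change in sample size. The related-events version costs slightly more because of the reconciliation.

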### 9.2 Primary outcome measures and sample size

The proposed study is a prospective, single-center, feasibility trial. The primary aim of this study is feasibility – specifically feasibility will be defined as completion of all study procedures over seven days. For the primary aim, we assume an acceptable completion rate from strata of MEC/HEC or tumor types of all study-related procedures would be at least 70%. Assuming a true completion rate of 85%, a sample size of 50 patients would have an 80% power to detect an absolute difference of 15% at Type I error 0.05.

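### The normal-approximation interval for complete response and the binary MAT items, read as a plain 95% Wald interval, covers too rarely near 0 or 1 at n=50 and can disagree with the planned z test against 90%

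*Combined protocol and SAP*

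**What the plan says.** Section 9.3(2), repeated in the Statistical Methodology part of the synopsis, describes the complete response proportion with "a one-sample confidence interval for proportions, applying the normal approximation to the binomial distribution". The same item adds a one-sample z test of whether the rate is "significantly different than the 90% seen in previous studies".

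Section 9.3(3) extends the interval to the MAT: "Binary variables will also be described using one-sample confidence intervals for proportions (as described in #2 above". Section 9.3(4) treats the FLIE outcomes as proportions, "using a 95% confidence interval to describe the proportion of participants with impacted QoL", and names no method.

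The planned size is 50 (section 4.1: "A total of 50 subjects, who are 18 years of age or older"), with no allowance for dropout. Three things are left open for items (2) and (3): which normal-approximation interval is meant, the confidence level (95% is written only in item (4)), and whether the z test uses the null or the sample variance. No exact or continuity-corrected form and no small-sample fallback is given.

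**The concern.** The usual interval under that description is Wald: the estimate plus or minus 1.96 estimated standard errors. Its standard error shrinks to nothing as the observed proportion nears 0 or 1, so with 50 patients the limits there are too narrow and can leave the 0-100% range. The plan's own benchmark for complete response, 90%, lies in that region.

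The textbook z test takes its variance from the null rate, whereas the Wald interval takes it from the data. Both are reported under the same item, and they can give opposite answers about 90%.

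Section 5.3 says that, if feasibility is met, the secondary results will be searched for an endpoint for a larger study. Limits that are too tight would overstate what 50 patients show.

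**Working it through.** **The plan's own figure.** The documents give no coverage figure. The only design figure is in section 9.2: "Assuming a true completion rate of 85%, a sample size of 50 patients would have an 80% power", against 70%, at Type I error 0.05. A one-sided z test with null variance reproduces it:

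Φ[(0.15 − 1.645·√(0.7·0.3/50)) / √(0.85·0.15/50)] = Φ[(0.15 − 0.1066)/0.0505] = Φ(0.859) = 80.5%.

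With the sample (alternative) variance the same test gives about 90.8%. The sample size was therefore probably worked out with the null variance. That is only a hint about the test in 9.3(2).

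**Inputs.** n = 50 (section 4.1); benchmark 0.90 (section 9.3(2)). Assumptions: Wald form, 95% level, two-sided test, null variance.

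**Formulas.**
- Wald: p̂ ± 1.96·√(p̂(1−p̂)/n).
- Coverage at a true rate p: the sum of Binomial(n, p) probabilities over every count x whose interval contains p.
- z = (x/50 − 0.90)/√(0.9·0.1/50) = (x/50 − 0.90)/0.04243.

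**Coverage at 90%.** The Wald interval contains 0.90 only for x = 40 to 47. It misses with probability P(X ≤ 39) + P(X ≥ 48) = 0.0094 + 0.1117 = 0.1211, so coverage is 1 − 0.1211 = 87.9%. Nearly all the misses are at 48-50 responders, where the lower limit lies above 90%.

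**Coverage elsewhere, n = 50, same enumeration.**

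| True rate | Wald | Wilson |
|---|---|---|
| 88% | 93.5% | 95.4% |
| 89% | 91.7% | 93.5% |
| 90% | 87.9% | 97.0% |
| 91% | 94.2% | 95.8% |
| 92% | 91.2% | 94.1% |
| 95% | 92.0% | 96.2% |
| 98% | 63.5% | 92.2% |

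Low rates mirror high ones (10% behaves as 90%). On a grid of 0.1 percentage points, Wald averages about 91% over 88-92% (range about 86-95%) and 93.7% over 15-85% (range 90.0-95.7%). With 42 evaluable patients, an assumed number, Wald coverage at 90% is 92.5%.

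**Interval against test at 90%.**

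| Responders | Wald interval | Contains 90%? | z | p |
|---|---|---|---|---|
| 40/50 | 0.80 ± 1.96·0.0566 = 68.9-91.1% | yes | −2.357 | 0.018 |
| 48/50 | 0.96 ± 1.96·0.0277 = 90.6-101.4% | no | 1.414 | 0.16 |
| 49/50 | 0.98 ± 1.96·0.0198 = 94.1-101.9% | no | 1.886 | 0.059 |

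At a true rate of 90% these results have probabilities 0.0152, 0.0779 and 0.0286, which sum to 0.122. At 70% the sum is 0.039, almost all from 40/50; at 60% it is 0.0014.

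**Boundaries.** The upper limit also passes 100% at 47/50 (100.6%). At 0/50 and 50/50 the interval is a single point; the exact interval at 0/50 is 0-7.1%.

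**Wilson.** This interval is the inversion of the null-variance z test. It contains 0.90 for x = 41 to 49, so it misses with probability P(X ≤ 40) + P(X = 50) = 0.0245 + 0.0052 = 0.0297. At the three results above it gives 67.0-88.8%, 86.5-98.9% and 89.5-99.7%, in agreement with the test each time.

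**The case against.** The strongest reply is that the troublesome region may never be reached. The 90% comes from a study of prevention after highly emetogenic chemotherapy (reference 17). This trial enrols patients in whom prophylaxis and first-line rescue have already failed. The only success figure the documents give for refractory nausea and vomiting is 70%, for olanzapine (section 1.2). Over true rates of 30-70%, Wald coverage averages 94.0% (range 92.1-95.7% on the same grid). The benchmark belongs to complete response alone, and nothing in the documents places the MAT items near 2%, 10% or 98%. These are also secondary, descriptive results with no go/no-go rule attached. All of this stands, and it limits the weight of the point.

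The second reply is that the plan never says Wald, never gives a level for these items and never gives the test's variance. With a continuity correction, coverage at 90% would be 96.3%. With the sample variance, test and Wald interval would agree by construction. This also stands, so both the coverage figures and the disagreement are conditional. It does not rescue the text, because a plan that leaves these choices open does not fix the analysis.

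A reader might infer that coverage is about 88% throughout the neighbourhood of 90%. It is not: 87.9% belongs to exactly 90% with exactly 50 patients, and coverage moves unevenly with both.

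**Conclusion.** The point holds in a limited form. If the interval is the plain 95% Wald interval, it falls short of its nominal level where the rate is near 0 or 1: by about 7 percentage points at the 90% benchmark with 50 patients, by 3 to 4 points on average over 88-92%, and by far more at 98%. It can also return limits above 100% or no width at all. If the z test also uses the null variance, interval and test give opposite answers about 90% at three possible results.

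At mid-range rates the shortfall is about one point and would not change any interpretation. The documents do not support reading this as a certain contradiction, as a demonstrated fault in the MAT results, or as a threat to the feasibility endpoint, which uses neither this interval nor the 90% benchmark. The change is worth making because it costs almost nothing and settles choices that the plan leaves open.

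**What to change.** In sections 9.3(2) and 9.3(3) and in the synopsis, replace the words naming the normal approximation with *Wilson score 95% confidence interval*. State that the one-sample z test is two-sided and uses the null variance. Name the same interval for the FLIE proportions in section 9.3(4), where no method is given.

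Interval and test then always agree at the matching level. Wilson coverage is not exactly 95% everywhere (93.5% at a true rate of 89%, 92.2% at 98%). If a guaranteed minimum of 95% is preferred, Clopper-Pearson is acceptable, but it does not invert the z test.

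The cost is a few words. No patients or data are added, and both R and SAS, named in section 9.4, provide the interval. The intervals will no longer be symmetric about the estimate and will be somewhat wider near 0 or 1: at 48/50 the width goes from 10.9 points (101.4 − 90.6, before rounding) to 12.4 points (98.9 − 86.5).

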### **5.5.3 Functional Living Index Emesis (FLIE) Scale**

The FLIE is a validated patient-reported measure of the impact of CINV on daily life, which measures a 5-day recall. The FLIE is a short, self-administered instrument containing two domains, one for nausea (nine items) and one for vomiting (nine items). Responses to each question are rated on a 100mm visual analog scale that is scored on a one to seven-point scale as described in the FLIE scoring manual. A higher score indicates a better quality of life. Minimal or no impact of CINV on daily life will be defined as an average score of more than six on the seven-point scale (i.e. 108 total score or greater than 54 domain score). The FLIE will be completed on the 5th day after CINV prophylaxis, and on the day of Akynzeo® treatment (Study Day 1). During the post-treatment observation portion of the study, the FLIE will be completed on Day 5 only. English and Spanish versions of the MAT will be made available at study activation. Additional foreign translations will be performed as needed.

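### FLIE is reported only as the proportion impacted at 54/108, with no summary of the scores and no before/after comparison, although scores are collected before and after dosing

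*Combined protocol and SAP*

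**What the plan says.** Section 5.5.3 describes the instrument: nine nausea items and nine vomiting items. "Responses to each question are rated on a 100mm visual analog scale that is scored on a one to seven-point scale", and higher is better. The same section ties minimal or no impact on daily life to "an average score of more than six on the seven-point scale (i.e. 108 total score or greater than 54 domain score"), citing the published five-day-recall version of the scale.

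Section 9.3, item (4), sets the analysis: "Quality of life will be analyzed as a binary response, impact on quality of life vs no impact". The impacted category is "a score of less than 54 on the FLIE domain scores and a score of less than 108 on the total score". Each of the three scores "will be analyzed separately using a 95% confidence interval to describe the proportion of participants with impacted QoL". The Study Summary repeats this. Neither place adds a summary of the scores themselves or a comparison between time points.

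On timing, section 5.5.3 schedules the FLIE on the fifth day after CINV prophylaxis and again on Study Day 1. "During the post-treatment observation portion of the study, the FLIE will be completed on Day 5 only".

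Elsewhere in section 9.3, the 0-10 MAT items receive a mean, an SD and an interval for the mean, and adverse event grade receives mean (SD) and median (IQR).

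**The concern.** An 18-item scale is reduced to one yes/no per patient, at a line close to the top of its range. A patient can improve a good deal without crossing that line, and the planned output would not show it. Nor does the plan say that the post-dose result is to be set against a pre-dose one, so even a crossing is not analysed as change.

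This matters because of how the data are to be used. Section 5.3 says that, if feasibility is shown, the secondary and exploratory results will be searched for an endpoint for a larger study. Judging whether the FLIE score could serve, and sizing a study on it, requires a mean, an SD and the SD of the change. The plan produces none of these from data that patients will already have supplied. Section 9.3 gives no reason for treating FLIE differently from the MAT scales.

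**Working it through.** **Inputs.** From section 5.5.3: 9 + 9 = 18 items, each scored 1 to 7, with an item average of 6 as the threshold. From sections 4.1 and 9.2: 50 patients. The documents give no FLIE mean, SD, correlation or sample-size figure.

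**1. The plan's own cut-offs reproduce.** 18 × 6 = 108 and 9 × 6 = 54.

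**2. Position of the cut-off in the range.** The total runs from 18 × 1 = 18 to 18 × 7 = 126, a span of 108 points. Each domain runs from 9 to 63, a span of 54. Below the cut-off lie (108 − 18)/108 = 90/108 = 83% of the total and (54 − 9)/54 = 45/54 = 83% of a domain.

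**3. What this means for one patient.** An item average rising from 3.0 to 5.9 takes the total from 54 to 106.2, a gain of 52.2 points, and the patient is impacted both times. A rise from 107 to 108, one point, changes the category.

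**4. Information kept by a binary split.** For a normal score cut so that a share q lies below the line, with c the normal quantile of q, the efficiency relative to the full score is φ(c)²/[q(1 − q)].

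| Share impacted | Efficiency | Equivalent of 50 patients |
|---|---|---|
| 50% | 0.637 | 31.8 |
| 70% (or 30%) | 0.576 | 28.8 |
| 80% | 0.490 | 24.5 |
| 90% | 0.342 | 17.1 |
| 95% | 0.224 | 11.2 |

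The loss passes one half at about 80/20.

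**5. Illustration of the range of consequences.** This was simulated with 2,000 runs of 50 pairs. Assumptions: normal scores limited to 18-126, pre/post correlation 0.5, two-sided 0.05. It compares an exact McNemar test at 108 with a paired t test on the score. The plan contains neither test; they only measure what each summary can show.

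| Assumed pre-dose mean (SD) | Mean rise | Impacted, before to after | Power at the cut-off | Power on paired change |
|---|---|---|---|---|
| 50 (20) | 20 | 99.8% to 97.1% | 0.5% | about 100% |
| 50 (20) | 30 | 99.8% to 91.9% | 18% | about 100% |
| 60 (20) | 20 | 99.2% to 91.9% | 16% | about 100% |
| 70 (20) | 20 | 97.1% to 81.6% | 70% | about 100% |
| 80 (25) | 20 | 86.9% to 62.6% | 87% | about 100% |
| 80 (25) | 30 | 86.9% to 46.8% | about 100% | about 100% |

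The cost of the cut ranges from almost total to negligible, depending on where scores start and how far they move.

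**6. Whether a paired change can be formed.** Two pre-dose FLIEs are planned, and neither is named as baseline. Section 6.0 places the Day 1 procedures before the capsule, which would make the Study Day 1 form pre-dose. However, section 5.5.3 gives only the day, and the FLIE footnote in the Schedule of Events mentions only fifth-day completions. The baseline needs naming.

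**7. Scores exactly on the line.** Section 5.5.3 asks for an average above six and a domain score above 54 before calling impact minimal. Section 9.3 counts only scores below 54 or 108 as impacted. A domain score of exactly 54 is therefore classed differently by the two sections.

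**The case against.** The cut-off is prespecified, sourced and easy to interpret. A responder proportion is a legitimate descriptive summary for a secondary outcome of a feasibility study. That stands, and nothing here calls for removing it.

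A reader might infer that nearly all patients will be classed as impacted, because all have CINV that broke through prophylaxis and rescue. The documents do not establish this. Eligibility accepts nausea or vomiting with no severity threshold, and a patient with nausea alone could score near the top of the vomiting domain. The only benchmark for refractory symptoms, in section 1.2, is a 70% success rate with a different drug on a different measure. If 30% were impacted, the split would keep 58% of the information, about 29 of 50 patients.

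A reader might also infer that dichotomising discards most of the information, or that it cannot register a large improvement. The first holds only beyond roughly 80/20 and under normality, which a bounded score may not follow. The second holds only for patients who improve yet stay below the line; those who cross it change category. The missing before/after comparison is a separate gap, and a mean at each visit would not by itself close it.

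Finally, the scores remain in the database, and the MAT items will supply some continuous symptom data. Both are true. But FLIE measures effect on daily life, which the MAT does not, and a score analysis added after the results are known carries less weight than one stated in advance.

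**Conclusion.** The point holds as a gap in a descriptive secondary analysis. Section 9.3(4) and the Study Summary plan only the proportion impacted, with no continuous summary and no comparison across time. The part that rests on the documents alone is that 83% of the range falls in one category, that improvement within that category is not shown, and that no mean, SD or change will be available for the endpoint search in section 5.3.

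The size of the statistical loss is conditional. It is at least 36% of the information under normality (the 50/50 case) and more than half beyond roughly 80/20. Where this trial will fall is unknown. The simulated figures rest wholly on assumed means, SDs and correlation.

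The cut-off itself is not shown to be wrong, and the primary feasibility conclusion is unaffected. With a single arm, a paired change would describe the patients' course and supply planning figures; it would not isolate an effect of the drug.

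**What to change.** In section 9.3(4) and the matching item of the Study Summary:

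- Keep the proportion impacted, with its 95% interval, for the total and each domain.
- Add mean, SD, median and IQR of the total and both domain scores at each scheduled completion.
- Name one pre-dose FLIE as baseline (for example Study Day 1, stated to be completed before the capsule). Report the paired change from it to Day 5 for the total and both domains, with the number of complete pairs, the SD of the change and a 95% interval for its mean.
- Align sections 5.5.3 and 9.3 on how scores of exactly 54 and 108 are classed.

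The cost is a few sentences and one table. No new form, visit or patient is needed, since the scores must be calculated anyway to apply the cut-off.
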